## Study Protocol

### Background and Significance

Complex, reconstructive, spinal fusion surgeries are associated with large amounts of blood loss. Antifibrinolytics, such as epsilon-aminocaproic acid, tranexamic acid(TXA), and aprotinin have been shown to reduce the blood loss and allogeneic, red cell transfusion requirements associated with these surgeries. Aprotinin has been withdrawn from the market, due to an association with renal toxicity. TXA is a lysine derivative that inhibits the formation of plasmin, thus inhibiting fibrinolysis, and is estimated to be 10 times more potent than epsilon-aminocaproic acid.

A meta-analysis of antifibrinolytic use in spine surgery found that TXA is effective in reducing blood loss, without an increase in medication related complications. Elwatidy *et al* performed a randomized, placebo-controlled study of a high dose TXA (2gm load, 100mg/hr infusion) for patients undergoing a variety of spinal surgeries. This study showed both the safety and efficacy of this regimen. The patients randomized to TXA suffered less blood loss ( $p = 0.007$ ) and required fewer PRBC transfusion ( $p = 0.008$ ). They note, however, that the small numbers (N=64) limit the conclusions and that a larger study of TXA in this patient population is needed.

In a retrospective analysis of patients undergoing complex spine reconstructions, Baldus *et al* were unable to show a significant difference in blood loss or transfusions requirements between patients receiving low dose TXA (10mg/kg load, 0.5mg/kg/hr infusion) and controls. These authors postulate that a higher dose may be more effective in reducing blood loss and transfusion requirements. This same group has presented data for complex pediatric spinal reconstructions, showing a high dose TXA regimen (100mg/kg load, 10mg/kg/hr) results in significantly less blood loss than control and similar results to aprotinin. No complications related to TXA were reported in either series.

Similar, effective results have been published in paediatric spinal deformity surgery. Grant *et al*, in a retrospective case-control series, showed a high dose TXA regimen (20mg/kg load, 10mg/kg/hr infusion) reduced blood loss and transfusion requirements when compared with a low dose TXA regimen (10mg/kg load, 1mg/kg/hr infusion). Unfortunately, the study was underpowered (High Dose TXA: 15, Low Dose TXA: 11) to detect a significant difference. Sethna *et al* showed a significant reduction in blood loss ( $p<0.01$ ) in paediatric patients undergoing spinal fusion for scoliosis. In both series, no complications were reported related to TXA use.

There is no appropriately powered study comparing two TXA dosing regimens in a homogenous patient population. This study will provide high quality evidence for or against the use of a high dose TXA regimen in adult spinal deformity patients, in addition to supporting the safety profile of TXA in this patient population.

### Research Design and Methods

Study Design: Randomized, double blind, controlled Trial at a single institution. The study will be registered at [www.ClinicalTrials.gov](http://www.ClinicalTrials.gov) .

**Power Analysis:** We anticipated an intraoperative estimated blood loss (EBL) of 2,000mL with a standard deviation of 500mL in the control group. A difference of 400mL was estimated to be a clinically relevant difference, as differences in excess of 400mL may result in additional units of allogeneic packed red blood cell transfusion during and after surgery. A sample size of 26 patients per group (52 total) was needed to find a difference of 400mL with a power of 80% and alpha defined as 0.05. In anticipation of nonadherence and loss to follow up, target enrollment was 60 patients.

**Selection Protocol:** Following Institutional Review Board (IRB) approval, adult patients (ages 18-75) scheduled to undergo long segment (Upper Instrumented Vertebra (UIV) T5 or proximal and Lower Instrumented Vertebra (LIV) L3 or distal) posterior spinal fusion with instrumentation (PSF) for adult scoliosis without a current deep venous thrombosis (DVT), TXA related contraindications, or other distinct contraindications are eligible and consent for participation will be sought.

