18. Visual Analog Pain Score

Intraoperative data collected will include:

1. Procedure Length (Incision to Skin Closure, minutes)
2. Levels Fused
3. Levels of Instrumentation and Type
4. Osteotomies Performed (Yes / No / Type)
5. Hemoglobin Concentration at Incision, Closure (by Arterial Blood Gas)
6. Estimated Blood Loss (estimated as three times cell saver volume)
7. Crystalloid / Colloid Volume Infused
8. Allogeneic Packed, Red Blood Cells (PRBC) / Fresh Frozen Plasma (FFP) / Platelets (PLT) Transfused
9. Urine Output
10. Intraoperative Surgical Complications

Postoperative data collected will include:

1. Drain Output (with Length of Drain Use)
2. CBC on Postoperative Days #1,2, and 3
3. Units of PRBC / FFP / PLT Transfused
4. Length of Hospital Stay
5. Disposition at Discharge
6. Acute Perioperative Complications
7. Duplex Ultrasound Scan of Lower Extremities Result

Followup visits will be six weeks and three months to capture complications potentially related to TXA at up to three months after surgery. At these visits, SRS-22 and ODI scores will be obtained. The dependent variables of interest are:

1. Intraoperative and Total Estimated Blood Loss
2. Number of PRBC Units Transfused
3. Intraoperative and Acute Complications (up to three months)

All findings will be reported using CONSORT guidelines.

Human Subjects

All protocol violations will be reported to the Washington University IRB. All serious adverse events (SAE's) will be reported to the Washington University IRB within 15 days of occurrence. SAE will be tracked and potential association with TXA administration will be determined site PI. Any frequently occurring SAE felt to be associated with TXA administration will be reported to all participating centers as well as Med Watch.

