Low versus High Dose Tranexamic Acid in Adult Spinal Deformity Surgery: A Randomized, Controlled Trial

NCT 02053363

08/01/2018

Statistical Analysis Plan

Parametric data were expressed as mean \pm standard deviation and compared using the Student t test and Chi-square. Nonparametric data were expressed as median (interquartile range) and compared via the Mann-Whitney U test. Prior to analysis, outlier values were examined to determine their origin and ensure they did not represent data entry errors. Enrollment and surgical data were compared to ensure successful randomization. Data were analyzed on an intention-to-treat basis. Only patients who enrolled and underwent surgery were considered completed. Randomization failures were patients who enrolled but failed to undergo surgery as scheduled and were not randomized. Mean EBL was the primary outcome measure, while number of PRBC transfused, mean number of intraoperative complications and 90-day complications were secondary outcomes. All tests were 2 sided and were considered statistically significant if the P value was less than 0.05. Statistical analysis was performed using JMP, version 13 (SAS Institute Inc., Cary, North Carolina, USA).

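### Does the lack of a stated rule for patients not seen at three months require a change to the plan?

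*Protocol*

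**What the plan says.** The Power Analysis paragraph of the protocol (Research Design and Methods) rests on one outcome: "We anticipated an intraoperative estimated blood loss (EBL) of 2,000mL with a standard deviation of 500mL in the control group". It seeks a 400 mL difference with 80% power at alpha 0.05, finds 26 per group, and then raises the total from 52: "In anticipation of nonadherence and loss to follow up, target enrollment was 60 patients". No rate of loss is given.

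The Data Collection lists record EBL as an intraoperative item, estimated as three times the cell saver volume. They give the later visits a different purpose: "Followup visits will be six weeks and three months to capture complications potentially related to TXA at up to three months after surgery".

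The SAP makes mean EBL the primary outcome. It adds that, besides red cell units, "mean number of intraoperative complications and 90-day complications were secondary outcomes". On populations it says "Data were analyzed on an intention-to-treat basis" and "Only patients who enrolled and underwent surgery were considered completed". The next sentence describes randomization failures: patients who enrolled, did not have surgery as scheduled and were not randomized. Neither document mentions a denominator, imputation or sensitivity analysis for patients missing at three months.

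**The concern.** The plan expects loss to follow-up and answers it with extra patients for an outcome that such loss cannot touch. For the outcome it can touch, the plan gives no rule. Extra enrolment replaces people; it does not supply their unseen outcomes.

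The SAP sentence on completion can also be read as calling every operated patient complete, whether or not anyone saw that patient at three months. Combined with intention to treat, this could lead an analyst to count a lost patient as having had no complication, which would make both regimens look safer. The protocol's Background says the study will produce efficacy evidence "in addition to supporting the safety profile of TXA in this patient population", so the safety comparison matters. A denominator left open until the data are in could also be chosen to suit the result.

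**Working it through.** **1. The plan's own sample size.** Inputs from the Power Analysis: difference 400 mL, SD 500 mL, so d = 400/500 = 0.8; power 80%; alpha 0.05. Two-sided testing comes from the SAP. The two-sample t test (noncentral t) needs 25.52 per group, rounded up to 26, which agrees with the protocol. Power is 80.7% at 26 per group.

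**2. The increase to 60.** The implied allowance is 1 − 52/60 = 13.3%, or 8 patients.

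- Loss after surgery removes no EBL value. With 30 operated per group, power is 86.1%.
- Enrolled patients who never reach surgery do reduce the number analysed. With 28 per group power is 83.6%; with 26 it is 80.7%.
- Departures from the regimen could dilute the contrast under intention to treat. With 30 per group and an assumed 5% dilution (d = 0.8 × 0.95 = 0.76), power is 82.5%.

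The surplus therefore serves the primary outcome, although one of the two reasons given for it does not apply there.

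**3. How much of the 90-day outcome could be unknown.** Assume 30 operated per arm, loss split equally, and no complication seen before loss.

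| Lost per arm | Unobserved share | Possible shift in the difference between arms |
|---|---|---|
| 1 | 1/30 = 3.3% | ±3.3 points |
| 2 | 2/30 = 6.7% | ±6.7 points |
| 4 (whole allowance) | 4/30 = 13.3% | ±13.3 points |

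With 3 observed events in an arm and 4 patients lost, the rate is 3/30 = 10.0% if the lost are counted as event-free, 3/26 = 11.5% if they are excluded, and 7/30 = 23.3% if all had an event. For comparison, the 95% sampling half-width of the difference, 1.96 × √(2p(1 − p)/30), is 15.2 points at an assumed p of 10% and 20.2 points at 20%. Even the extreme shift in the table is smaller than the sampling uncertainty already present.

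**4. Can the denominator decide significance?** It can, but seldom. Take 9 v 3 patients with a complication and 4 lost per arm. The uncorrected chi-square is 3.75 (p = 0.053) on 30 per arm and 3.90 (p = 0.048) on 26. Fisher's exact test gives 0.104 and 0.097, so it does not cross 0.05.

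There are 16 × 17/2 = 136 event pairs with 0 to 15 events per arm, larger count first. Comparing 30 per arm with the reduced denominator, the chi-square crosses 0.05 in:

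- 0 pairs with 1 lost per arm;
- 1 pair with 2 lost per arm;
- 3 pairs with 4 lost per arm (9 v 3, 13 v 6, 14 v 7).

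With 4 lost per arm and events drawn binomially among the 26 observed, the probability of a crossing table is 0.02% at true rates of 10% in both arms, 0.9% at 20% in both, 0.8% at 20% v 10%, and 3.3% at 30% v 10%.

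**5. What the completion sentence says.** "Only patients who enrolled and underwent surgery were considered completed" states a necessary condition: nobody without surgery is complete. It does not say that everyone with surgery is complete, and it assigns no outcome to anyone. It stands next to the definition of randomization failures, and its natural purpose is to separate operated from non-operated enrolees.

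**The case for a change.** The strongest case for a change is that the gap is real and cheap to close. The SAP is one short paragraph with no rule for this outcome. The safety aim is explicit, and if the plan's whole allowance were lost after surgery, 13.3 points of each arm's rate would be unobserved. Counting the lost as event-free can only lower the observed rates. A few sentences and two sensitivity analyses would settle the matter without extra patients.

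Much of this stands. The 90-day denominator is unstated, and the loss-to-follow-up reason has no bearing on EBL. Four points limit it:

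- The 13.3 points is an upper bound on an assumed loss. The protocol also collects acute perioperative complications and a lower-extremity duplex result, and it tracks serious adverse events, so some complications in patients who miss a visit would still be known.
- The SAP may intend a mean number of complications per patient at 90 days as well as during surgery. The proportions above are then only an illustration.
- The usual remedy, keeping all operated patients with complications recorded up to last contact, also treats unseen time as event-free. It would disclose the possible bias but would not remove it.
- The protocol commits to CONSORT reporting, although that supplies no handling rule of its own.

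**Conclusion.** No change is needed. No stated figure or rule is wrong: 26 per group reproduces, 60 stands, and removing loss to follow-up from the reasons for the surplus would alter no analysis. What remains is an unwritten detail for one unpowered secondary outcome. It could leave at most 13.3 points of each arm's rate unknown, assuming 30 operated per arm and four unobserved in each. A sensible analyst would give the numbers operated and assessed by arm and state the denominator used. The reading that the SAP codes lost patients as free of complications goes beyond its text. The 0.05 crossing is a selected case: 3 of 136 event pairs at the largest loss considered, and none with one lost per arm. The documents give neither a loss rate nor a complication rate, so these sizes rest on the stated assumptions.

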#### Contraindications to Tranexamic Acid

1. Patients with an acquired defective color vision
2. Patients with subarachnoid hemorrhage
3. Patients with active intravascular clotting
4. Patients with hypersensitivity to tranexamic acid or any of the ingredients

#### Contraindications to Enrollment

1. Any patient who pre-donates autologous blood for intra- or postoperative use. (Directed donor units are acceptable).
2. Any patient with history of suspected blood disorders or abnormal coagulation laboratory results.
3. Any patient on anticoagulation therapy that cannot be interrupted.
4. Any patient with history of deep vein thrombosis (DVT).
5. Any patient with impaired renal function or serum creatinine > 1.5.

All eligible patients will be provided with a detailed explanation of the study as well as a copy of an Investigational Review Board (IRB) approved informed consent form to take home and review. Only after all patient questions have been answered and the patient is agreeable to participation, will an informed consent be obtained. A study coordinator will obtain and complete baseline data forms.

**Patient Randomization:** After consent is obtained and the patient is enrolled in the trial, patients will be assigned deidentified, unique ID numbers. Randomization of these IDs to either low or high dose tranexamic acid will occur via a computer generated random assignment. Given the variations that may exist in surgical technique (e.g. performance of osteotomies), stratified randomization will be performed by attending surgeon. Based upon the randomization, the pharmacy will prepare tranexamic acid (TXA) for one of two intravenous dosing protocols(independent variable): (1) Low Dose(Standard of Care/Control): Loading Dose 10mg/kg given over 15 minutes, followed by 1mg/kg/hr via continuous infusion (2) High Dose(Study Group): Loading Dose 100mg/kg given over 15 minutes, followed by

10mg/kg/hr via continuous infusion. The medications will be delivered to the operating room in identical packaging for both treatment groups, and labeled "TXA Study Drug." All patients will receive a test dose prior to the induction of general anesthesia. The surgeon, anesthesia team, and operating room staff will be blind to the concentration of TXA in the medications received. Treatments may be "unblinded" at the discretion of the surgeon and anesthesiologist, in cases of extreme blood loss. If additional anti-fibrinolytics are given, the change in dose will be recorded. The loading dose will be given to coincide with incision. The continuous infusion will be stopped at the conclusion of fascial layer closure.

**Surgical Technique:** A standard, midline, subperiosteal approach will be taken to the spine. Hemostasis will be achieved with electrocautery. Mean arterial pressures (MAP) will be maintained between 60-80mmHg in an effort to minimize blood loss. At the discretion of the surgeon, posterior column osteotomies and three column osteotomies/vertebral column resections will be performed. When performed, the number and location will be recorded. Pedicle screw instrumentation will be used preferentially. Extension to the ilium will accompany any lumbosacral fusion. Standard reduction techniques will be used. The dorsal elements will be decorticated, as a last measure. Iliac crest will not be harvested, unless specifically requested by the patient, or if a contraindication to the use of bone morphogenetic protein-2 (rhBMP-2) exists. Intraoperative red blood cell salvage will be used. Subfascial and suprafascial drains will be placed routinely. All wounds will be closed routinely, in layers. Drains will be removed on postoperative day #3 or when output is 30cc or less over an 8 hour shift.

**Postoperative Protocol:** All patients are mobilized on postoperative day #1. Complete blood counts (CBC) are obtained on postoperative days #1-3. A transfusion trigger for all patients will exist at a Hemoglobin level of 8.0 g/dL. Patients with a higher hemoglobin level, with symptomatic anemia, who are refractory to fluid repletion will receive allogeneic red cell transfusions. All patients are kept nothing by mouth until a return of bowel function. Until diets are advanced, patients will receive intravenous maintenance fluids. All patients receive respiratory therapy postoperatively, to include incentive spirometry and intermittent positive pressure breathing.

**Data Collection:** Routine demographic data will be collected at enrollment:

1. Age
2. Weight (kg)
3. Height (cm)
4. Gender
5. Race
6. Primary Diagnosis
7. Standard Scoliosis Research Society Radiographic Measurements
  - a. Coronal / Sagittal Cobb Measurements
  - b. Coronal / Sagittal Alignment by C7 Plumb Lines
8. Charlson Comorbidity Index
9. American Society of Anesthesiologists' (ASA) Score
10. Nicotine Status

11. Complete Blood Count
12. Coagulation Profile (PT/PTT/INR)
13. Narcotic Use (None / Mild Narcotic / Strong Narcotic / Quantities)
14. Allergies
15. Preoperative Neurologic Exam
16. Scoliosis Research Society – 22 Score
17. Oswestry Disability Index Score
18. Visual Analog Pain Score

Intraoperative data collected will include:

1. Procedure Length (Incision to Skin Closure, minutes)
2. Levels Fused
3. Levels of Instrumentation and Type
4. Osteotomies Performed (Yes / No / Type)
5. Hemoglobin Concentration at Incision, Closure (by Arterial Blood Gas)
6. Estimated Blood Loss (estimated as three times cell saver volume)
7. Crystalloid / Colloid Volume Infused
8. Allogeneic Packed, Red Blood Cells (PRBC) / Fresh Frozen Plasma (FFP) / Platelets (PLT) Transfused
9. Urine Output
10. Intraoperative Surgical Complications

Postoperative data collected will include:

1. Drain Output (with Length of Drain Use)
2. CBC on Postoperative Days #1,2, and 3
3. Units of PRBC / FFP / PLT Transfused
4. Length of Hospital Stay
5. Disposition at Discharge
6. Acute Perioperative Complications
7. Duplex Ultrasound Scan of Lower Extremities Result

Followup visits will be six weeks and three months to capture complications potentially related to TXA at up to three months after surgery. At these visits, SRS-22 and ODI scores will be obtained. The dependent variables of interest are:

1. Intraoperative and Total Estimated Blood Loss
2. Number of PRBC Units Transfused
3. Intraoperative and Acute Complications (up to three months)

All findings will be reported using CONSORT guidelines.

Human Subjects

All protocol violations will be reported to the Washington University IRB. All serious adverse events (SAE's) will be reported to the Washington University IRB within 15 days of occurrence. SAE will be tracked and potential association with TXA administration will be determined site PI. Any frequently occurring SAE felt to be associated with TXA administration will be reported to all participating centers as well as Med Watch.

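### Surgeon strata leave within-surgeon variation in osteotomy to chance and the SAP compares EBL unadjusted: this costs precision, not validity, and a prespecified adjusted model would recover some of it

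*Protocol*

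**What the plan says.** - **Stratification.** Protocol, Patient Randomization: "Given the variations that may exist in surgical technique (e.g. performance of osteotomies), stratified randomization will be performed by attending surgeon". No other factor is named. The number of surgeons and any block size are not given.
- **Osteotomies.** Protocol, Surgical Technique: "At the discretion of the surgeon, posterior column osteotomies and three column osteotomies/vertebral column resections will be performed". Their number and location are to be recorded, and the intraoperative data list includes "Osteotomies Performed (Yes / No / Type".
- **Eligibility.** Protocol, Selection Protocol: "long segment (Upper Instrumented Vertebra (UIV) T5 or proximal and Lower Instrumented Vertebra (LIV) L3 or distal) posterior spinal fusion with instrumentation (PSF". This sets a minimum extent of fusion. Neither it nor the exclusion lists mention osteotomy.
- **Analysis.** SAP: parametric data are "compared using the Student t test and Chi-square"; nonparametric data go to a Mann-Whitney test. There is no model and no term for surgeon, osteotomy or levels. Enrolment and surgical data are compared between arms as a check on randomisation, with no stated consequence if they differ.
- **Sample size.** Protocol, Power Analysis: control-group mean EBL 2,000 mL, SD 500 mL, difference 400 mL, 80% power, alpha 0.05, 26 per group, target enrolment 60. The SAP makes all tests two-sided.

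**The concern.** The Protocol recognises that osteotomies may vary and treats technique variation as worth controlling, but the factor it controls is one step removed. If a surgeon's eligible cases include both fusions without osteotomy and three-column procedures, strata defined by surgeon do nothing about which of those patients go to which arm. The analysis does not take it up either, because the t test and the Mann-Whitney test use no patient characteristics.

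What is at stake is efficiency. If major osteotomy adds materially to blood loss, the variance between case types stays in the error term of the primary comparison, although part of it could be predicted from the surgical plan before randomisation. In a trial of 52 to 60 patients sized for a single 400 mL difference, that gain is worth having. The between-arm check in the SAP can reveal an imbalance but does not recover any precision.

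**Working it through.** **1. The plan's own figure.** Two-sample t test, two-sided alpha 0.05, difference 400 mL, SD 500 mL (standardised difference 400/500 = 0.8). The noncentral t calculation gives 25.5 per group, rounded up to 26, with power 80.7% at 26. The stated sample size reproduces.

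**2. What surgeon strata achieve.** Assumptions, since the documents give none of these: 4 surgeons, permuted blocks of 4, 52 patients, 8,000 simulated trials. SD of the between-arm difference in osteotomy rate, in percentage points:

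| Osteotomy rates across surgeons | No strata | Surgeon strata |
|---|---|---|
| 30% for every surgeon | 12.5 | 12.7 |
| 10%, 20%, 40%, 50% | 12.6 | 12.0 |
| 0%, 0%, 60%, 60% | 12.7 | 9.7 |

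Surgeon strata help to the extent that surgeons differ in how often they perform osteotomies, and not otherwise.

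**3. Where the variance sits.** Let p be the proportion with a three-column procedure and d the extra EBL it brings. Both are assumptions: p = 20%, d = 500 to 1,000 mL. The between-case-type variance is p(1 − p)d² = 0.16d².

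*Reading A: 500 mL is the overall SD of the control group.* Unadjusted power is 80.7%. Adjustment removes 0.16d² from the error variance:
- d = 500: √(250,000 − 40,000) = 458 mL, power 87.0%
- d = 750: √(250,000 − 90,000) = 400 mL, power 94.2%

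At d = 1,000 the case-type term would be 160,000 of the 250,000 mL² total, leaving a residual SD of 300 mL and power of 99.7%. I do not rely on that figure: one yes/no factor explaining 64% of the variance is a strong assumption.

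*Reading B: 500 mL is the SD within one case type.* The unadjusted SD is then larger:
- d = 500: √(250,000 + 40,000) = 539 mL, power 74.7%
- d = 1,000: √(250,000 + 160,000) = 640 mL, power 59.8%

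Full adjustment returns the SD to 500 mL and power to about 81%.

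All powers are for 26 per arm. If all 60 patients were analysed (30 per arm), Reading B would give 80.7% at SD 539 and 66% at SD 640.

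**4. The chance shift is not an extra harm.** Under Reading A the standard error of the difference at 26 per arm is 500 × √(2/26) = 139 mL. Chance imbalance in case type contributes d × √(2 × 0.16/26), which is 55 mL at d = 500. The rest contributes 458 × √(2/26) = 127 mL. Since 55² + 127² ≈ 139², the imbalance is a component of the standard error that the unadjusted test already uses, not an addition to it.

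**The case against.** The strongest reply is that nothing here is broken. Randomisation balances case type in expectation, and the unadjusted test allows for chance imbalance and keeps its error rate. This stands.

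The Protocol offers osteotomy as one example of technique variation, not as the sole target of stratification. Because osteotomy is discretionary, surgeon is a reasonable stratifier. This also stands: where surgeons differ sharply, surgeon strata cut the imbalance SD from 12.7 to 9.7 points. It does not reach variation within a surgeon's own cases, which the Protocol permits; how large that variation is, the documents do not say.

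The Power Analysis attaches the 500 mL to the control group, which most naturally means all patients in that arm. That makes the power shortfall conditional on the less natural reading.

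The adjusted powers treat the plan as a perfect guide to what is done. Since the surgeon may depart from it, they are upper bounds.

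A reader might also infer that the trial contradicts its own claim to a uniform population, because the Background says: "There is no appropriately powered study comparing two TXA dosing regimens in a homogenous patient population". That sentence describes a gap in the literature and follows citations of mixed and paediatric series. It is not an eligibility standard that the plan then fails.

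What survives is narrower: a baseline predictor of blood loss, implied by the Protocol's own reasoning, is not used in the analysis.

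**Conclusion.** The point holds as a loss of precision that the analysis could partly recover. If 500 mL is the overall SD, the trial has its planned 80.7% power at 26 per arm, and adjustment would lift this to at most about 87% (500 mL extra loss) or 94% (750 mL). If 500 mL is a within-case-type SD, unadjusted power at 26 per arm would be about 75% (500 mL) or 60% (1,000 mL). The 20% rate and the extra losses are assumptions; the documents give neither, and they do not settle which SD is meant.

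Two stronger conclusions are tempting and unsupported. One is that the treatment comparison is biased or the test invalid: allocation is random, so it is neither. The other is that the trial is underpowered: that needs the less natural reading of the SD together with the assumed rate and extra loss.

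**What to change.** In the SAP, replace the unadjusted primary comparison of EBL with a prespecified linear model containing treatment, planned three-column osteotomy or vertebral column resection (yes/no) and planned number of levels. Take both covariates from the pre-operative plan documented before randomisation. Do not use the osteotomies performed: these are recorded during surgery, after allocation, and are discretionary. The planned upper and lower instrumented vertebrae are already needed to apply the eligibility rule, so planned levels should be obtainable.

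The cost is two baseline fields to record or abstract and about two degrees of freedom (50 to 48 with 52 patients). The SAP is dated 08/01/2018 and written in the past tense, so enrolment may be over. The values could then be abstracted from dated pre-operative records. If outcomes by arm have already been seen, the adjusted result should be reported as supplementary and labelled as such.

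I would not ask for planned osteotomy as a second stratification factor. With about 60 patients already divided by surgeon it thins the strata, and the model captures the precision gain without that.
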